DESIGN: A nationwide stepped wedge cluster randomised trial in which primary care midwifery practices will be randomised.

PARTICIPANTS: 15,000 women who receive/continue care in the participating midwifery practice after the 20 week structural ultrasound and who have a singleton pregnancy.

INTERVENTION AND CONTROL STRATEGIES: In all midwifery practices, growth will be monitored using standardised symphysis fundal height (SFH) measurement. In the intervention strategy two routine US examinations will be performed (between 28-30 weeks and 34-36 weeks), while in the control strategy US examination will only be performed when clinically indicated. In both groups the IRIS consensus-based protocol will be followed if intrauterine growth retardation is suspected.

PRIMARY OUTCOMES: The clinical primary outcome is a dichotomous composite measure 'severe adverse perinatal outcome' up to 7 days after birth, including: perinatal death; Apgar score below 4 at 5 minutes after birth; impaired consciousness; need for assisted ventilation for more than 24 hours; asphyxia; septicaemia; meningitis; bronchopulmonary dysplasia; intraventricular haemorrhage; cystic periventricular leukomalacia; neonatal seizures or necrotizing enterocolitis. Also direct and indirect costs are primary outcomes.

SAMPLE SIZE: A total of 15,000 women in 60 midwifery practices; 7,500 women per strategy.

MAIN DATA ANALYSIS AND ECONOMIC EVALUATION: Multivariable logistic regression analyses, taking into account the clustered design. The economic evaluation will consist of a cost-effectiveness and a cost-utility analysis and will be performed from both a health care provider and societal perspective. We will base all primary analyses on intention to treat.

DURATION: 48 months.

Problem definition

DETECTION OF SMALL-FOR-GESTATIONAL-AGE

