The IRIS study is designed as a stepped wedge cluster randomised trial (c-RCT, Figure 1). A stepped wedge design is a type of crossover design in which different clusters cross over (switch treatments) at different time points. Clusters cross over in one direction only; typically from control to intervention. The time at which a cluster starts with the intervention is randomized; more than one cluster may start the intervention at a particular time point [Hussey 2007]. The advantages of a stepped wedge design are: a) all practices will offer the intervention for a shorter or longer period of time, which may encourage them to take part, b) practices will serve as their own control for a variable time period which will reduce the variation in characteristics and practice management between the intervention and control strategy group. Note: in contrast to many other stepped wedge c-RCTs the women participating in our study will receive the intervention strategy OR control strategy.

Midwifery practice will be the unit of randomisation. Randomisation per practice rather than per midwife or client has the advantage of minimising contamination and therefore maximising contrast between the intervention and control strategy group.

All midwifery practices (n=60) will start in the control strategy and provide obstetric care as usual. At intervals of 3 months, 33,3% of all practices (n=20) will change status from control to intervention group and will start offering the intervention, i.e. routine biometry ultrasound in the third trimester of pregnancy. To balance the number of women in the intervention and control group, practices will be stratified prior to randomisation in large and small practices, with the average practice size as the cut-

off point (i.e. 250 clients a year). Within these two strata, a computer-generated random sequence will determine the order in which practices move from control to intervention status. This randomisation will take place after practices have been recruited for participation in the study and before data collection begins.

Figure 1: The IRIS stepped wedge design | UC = control strategy; INT= intervention strategy; US= ultrasonography

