Clients will be recruited during months 1-12 (at 20-22 weeks gestation). During months 13-16 clients who are recruited last will receive their routine US (at 28-30 weeks and 34-36 weeks gestation). In month 17 the last IRIS study babies will be born. Follow-up measurement will take place in months 18-23.

SELECTION CRITERIA, RECRUITMENT, AND INFORMED CONSENT

Midwifery practices

Practices are eligible if they meet the IRIS study quality criteria of fetal ultrasonography. Furthermore, only practices where all midwives have received (or: agree to soon receive) the post registration training on the new KNOV guideline 'detection of IUGR' will be included in our trial.

Midwifery practices may show interest to participate in our RCT via a question in our nationwide survey on detection and management of suspected IUGR (sub-study A). Additionally, we will attend meetings of regional maternity care networks (the so-called VSVs) to inform and invite members to participate in our randomized trial. Other methods to inform midwifery practices about the IRIS study will be the post registration training sessions within the context of the new KNOV guideline; via the newly founded Midwifery Research Network Netherlands (MRNN) which is part of the midwifery consortium; articles in the journals of the national professional organisations; via social media.

All midwifery practices that show interest will be visited by a researcher who will inform them about the study's aims and procedures, will check if the practice fulfils the inclusion criteria, and if so, ask the midwives to sign a contract to show their commitment to the study protocol, in particular to the use of US according to randomisation status and use of the IRIS consensus-based protocol.

Pregnant women

In participating practices, pregnant women will be handed an information leaflet on the IRIS-study by their midwife during the first consultation after the 20 week screening test. Inclusion criteria: receiving/continuing care in the participating midwifery practice after the 20 week screening test and

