Given the above mentioned ICCs for neonatal mortality, the formula to correct for clustering $[1 + (n-1) * ICC]$ with $n = 250$ (i.e. average cluster size) gives a required sample size for the IRIS study of 14,547 (ICC 0.0003) to 20,304 (ICC 0.002). For two reasons we expect the ICC in the IRIS study to be much more similar to 0.0003 than to 0.002. Our first argument is that the ICCs reported in the paper of Pagel et al. (2011) are based on prevalence rates ranging from 1.5% to 5.9% which is higher than the expected severe perinatal outcome in the IRIS study. As ICCs are associated with the prevalence of the outcome of interest [Pagel et al., 2011] we may expect the ICC in the IRIS study to be even lower than 0.0003. Our second argument is that midwife practices will offer both the control strategy (i.e. US on indication) and, later on, the intervention strategy (i.e. routine US). This will reduce the variation in characteristics and practice management between the intervention and control strategy group and thereby lower the size of the ICC .

Taking into account an ICC of 0.0003, the required sample size is 14,547 women. As not all women who will sign the informed consent form may receive care in the participating midwifery practice at the start of the third trimester, we adjusted this figure to a total of 15,000.

Effectiveness analyses

Firstly, we will assess the similarity between baseline characteristics of women having had the intervention strategy and women having had the control strategy. Secondly, we will compare baseline characteristics of drop-outs and completers by using logistic regression analysis. Thirdly, we will use multivariable logistic multilevel analyses to investigate the effect of routine US screening on perinatal outcome, adjusting for possible clustering of observations and confounders (e.g. ethnicity, maternal age, weight and height, smoking, alcohol use, drug use, blood pressure). We will base our analyses on intention to treat and set the level of significance at $p < 0.05$.

We will perform a subgroup analysis for women without US indication and for nulliparous women.

In addition to the intention to treat analysis we will also perform a per-protocol analysis, restricted to the women in the intervention group who received the two US examinations and to the women in the control group who did not receive any screening US.

Cost-effectiveness and cost-utility analyses

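### The stated effectiveness model names no period term although strategy is confounded with calendar time by design, and the power is not stated for a model that has one

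*Protocol*

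**What the plan says.** Under Study design, the Protocol sets out a stepped wedge in which "Clusters cross over in one direction only; typically from control to intervention". All 60 practices begin in control, and "At intervals of 3 months, 33,3% of all practices (n=20) will change status from control to intervention group". Recruitment is fixed in the next section of text: "Clients will be recruited during months 1-12 (at 20-22 weeks gestation".

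The analysis is described twice. The summary gives "Multivariable logistic regression analyses, taking into account the clustered design". The section Effectiveness analyses gives multilevel logistic models, "adjusting for possible clustering of observations and confounders (e.g. ethnicity, maternal age, weight and height, smoking, alcohol use, drug use, blood pressure", on an intention-to-treat basis at the 5% level. Every covariate listed is a characteristic of the woman. Neither place mentions period, step, calendar time or secular trend, and nor does the rest of the section Statistical analyses.

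The section Sample size of full trial starts from 13,536 women and multiplies by 1 + (n − 1) × ICC with n = 250. That is the design effect for a parallel cluster trial, and it contains no allowance for period.

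**The concern.** In a one-way rollout, the first quarter of recruitment is all control and the last is all intervention. Time and strategy are therefore associated by construction, whatever the randomised order of the practices. A practice random intercept removes stable differences between practices, and maternal covariates remove differences in case mix. Neither removes a change over time that all practices share.

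Study design presents practices serving as their own controls as an advantage. It does not note that this part of the comparison is before versus after. If the outcome rate drifts for any reason other than routine ultrasound, part of that drift is attributed to ultrasound, in either direction. The stated 5% level is then not the actual level.

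Power is also at stake. The standard remedy costs much of the precision on which 15,000 women was justified.

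**Working it through.** **The plan's own figures.** Inputs: 1.54% versus 1.0%, 80% power, significance level 0.05 (Sample size of full trial). The two-proportion formula, two-sided with pooled variance, gives 6,749 per group, 13,498 in total. This is within 0.3% of the stated 13,536. Then 13,536 × (1 + 249 × 0.0003) = 13,536 × 1.0747 = 14,547, as stated. At ICC 0.002, 13,536 × 1.498 = 20,277; the stated 20,304 is 13,536 × 1.5. The plan's figures therefore reproduce as a parallel-cluster calculation.

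**Layout (assumption).** Figure 1 is not shown. Three steps 3 months apart within 12 months of recruitment are read as four equal periods. With 15,000 women in 60 practices, that is 250 per practice and 62.5 per practice-period.

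| Period (midpoint, months) | 1.5 | 4.5 | 7.5 | 10.5 |
|---|---|---|---|---|
| Practices in control | 60 | 40 | 20 | 0 |
| Practices in intervention | 0 | 20 | 40 | 60 |

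Mean time, control: (60×1.5 + 40×4.5 + 20×7.5)/120 = 3.5 months. Mean time, intervention: (20×4.5 + 40×7.5 + 60×10.5)/120 = 8.5 months. The gap is 5 months, or 1.67 periods.

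**How much of a linear trend enters without a period term.** Generalised least squares with a practice random intercept and no period term passes 1.67 periods of trend into the effect at ICC 0, 1.69 periods (5.1 months) at ICC 0.0003 and 1.77 periods (5.3 months) at ICC 0.002. With period fixed effects it passes 0.

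**Consequence with no true effect.** The trend r is the assumed annual fall in the odds. Bias in log OR = 1.686 × ln(1 − r)/4. The standard error of the log OR with 7,500 per strategy at 1.54%, ignoring clustering, is √[2/(7,500 × 0.0154 × 0.9846)] = 0.133. The rejection rate uses the normal approximation.

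| Assumed fall per year | Bias in log OR | Spurious OR | Two-sided rejection |
|---|---|---|---|
| 10% | −0.044 | 0.96 | 6.3% |
| 20% | −0.094 | 0.91 | 10.9% |
| 30% | −0.150 | 0.86 | 20.5% |

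For scale, the target OR is (0.010/0.990)/(0.0154/0.9846) = 0.646. Producing that from trend alone would need a fall in the odds of about 65% per year.

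**Price of period terms.** At ICC 0 this can be done by hand. Each period has 3,750 women.

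- Without period, the information on strategy is proportional to 15,000 × ½ × ½ = 3,750.
- With period, only periods 2 and 3 contribute: 2 × 3,750 × (1/3 × 2/3) = 1,667.
- The variance ratio is 3,750/1,667 = 2.25.

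With the outcome variance taken at the mean rate, 0.0127 × 0.9873 = 0.01254, and a difference of 0.0054:

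| ICC | SE without period | SE with period | Variance ratio | Power without | Power with |
|---|---|---|---|---|---|
| 0 | 0.00183 | 0.00274 | 2.25 | 84% | 50% |
| 0.0003 | 0.00184 | 0.00278 | 2.28 | 83.5% | 49% |
| 0.002 | 0.00188 | 0.00293 | 2.43 | 82% | 45% |

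Adding practices at 62.5 women per practice-period, 80% power would need about 15,000 × 2.08 = 31,200 women at ICC 0.0003, or 15,000 × 2.31 = 34,700 at ICC 0.002.

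**The case against.** The strongest reply is that the covariate list is introduced as examples, so period is unnamed and not excluded, and that a full covariate specification usually belongs in an SAP, which is not shown here. The first part stands: a reader might infer that the plan rules out adjustment for time, and the text does not say that. The second part does not dispose of the point. The Protocol chose to state the model and the kind of confounder it has in mind, and it omitted the one confounder that its design guarantees. The sample size also has no allowance for period. An SAP that added period later would leave the Protocol's justification for 15,000 women unsupported.

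A second reply is that no trend in the outcome has been shown. That also stands. A reader might infer that the trial's type I error is definitely above 5%. It is so only if the outcome rate changes over the year, and the Protocol does not quantify such a change. The background reports that routine third-trimester ultrasound is increasing, which concerns practice and not the outcome rate.

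A reader might also take the eligibility wording, "only practices where all midwives have received (or: agree to soon receive) the post registration training", as proof that the trial creates its own trend. It allows training to be pending when a practice agrees to take part. It does not say that training follows the first enrolment, or that training changes the outcome. It is a possible source of drift and no more.

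**Conclusion.** The point holds as an omission with a conditional bias and a definite consequence for power. The described model has no stated protection against a shared time trend, and about 5 months' worth of any linear trend passes into the effect estimate. It would be too strong to say that all secular change is counted as an ultrasound effect: comparisons between practices within periods 2 and 3 are concurrent and dilute it. For the primary outcome, modest trends give modest bias, and only an implausibly steep one would imitate the whole target effect.

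The power result does not depend on any trend being present. Once period is in the model, the planned 15,000 women give about 45% to 49% power over the Protocol's own ICC range, against the stated 80%. These figures rest on four equal periods, equal practice sizes, a constant within-practice correlation and a normal approximation on the risk-difference scale. No size is claimed for secondary outcomes, because the Protocol gives neither their rates nor their trends.

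**What to change.** State the primary model as a logistic mixed model with strategy, fixed effects for the 3-month periods, a random intercept for practice and the baseline covariates. Since "practices will be stratified prior to randomisation in large and small practices", the size stratum may be added as a randomisation factor; this is optional and not essential to the point. Use the same period terms for the other outcomes compared by strategy.

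Replace the parallel-cluster calculation with a stepped wedge calculation that includes period, over the ICC range already cited. Then either report the power that 15,000 women provide or revise the size or layout of the trial.

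The wording change is a few sentences. The real cost is stated precision: the variance rises about 2.3 times and the standard error about 1.5 times, so the claim of 80% power for 1.54% versus 1.0% cannot be kept at the current size. In return, the estimate is free of any time trend shared by all practices.

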having a singleton pregnancy. The midwife will ask the woman if she is willing to participate in the IRIS study and if so, the midwife will ask her to sign the consent form. The form asks the woman's permission for using her personal data for merging data, for collecting detailed information from the woman's and her baby's client records, and for approaching her in the context of future sub-studies. An extra consent form will be added among the subsample of women who will fill in questionnaires. Consent forms will contain name, address, postal code, telephone number, and email and will be kept separate from other data files in a secure place.

Inclusion criteria: receiving

Women who do not have had a dating US will only be included if they have a reliable estimated data of delivery (EDD) based on the first day of their last menstrual period.

The NVOG guideline on US dating of pregnancy will be used for estimation of the EDD.

CONTROL AND INTERVENTION US STRATEGIES

Women in both US strategies will receive routine care as follows:

- Standardised SFH measurement
- Information about life style factors that may influence foetal growth, such as smoking, use of alcohol and drugs, and labour circumstances.
- Advise to report a reduction in fetal movements.
- US examinations on indication

Subsequent protocolised management will be according to the IRIS consensus-based protocol (to be developed in sub-study A).

Intervention US strategy

Additionally, two routine third trimester US examinations will be performed, one between 28 and 30 weeks and one 6 weeks after the first US. By performing two US examinations the growth pattern can be monitored. If a baby does not follow the expected curve, this may indicate a lack of growth even before the abdominal circumference or the estimated fetal weight is low. Subsequent protocolised management will be accomplished according to the IRIS consensus based guidelines.

PRIMARY OUTCOME - SEVERE ADVERSE PERINATAL OUTCOME

The primary clinical outcome is the occurrence of any severe adverse perinatal outcome up to 7 days after birth (yes/no). It concerns a dichotomous composite measure with 'yes' being defined as the presence of one or more of the following:

1. Antepartum, intrapartum or neonatal death occurring from 28 weeks gestation
2. Apgar score below 4 at 5 minutes after birth;
3. Coma, stupor or decreased response to pain;
4. Asphyxia, defined as cord blood arterial base excess of less than minus 12;

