Characteristics of midwifery practice, as presented in the latest LVR report

- number of midwives working in the practice
- number of clients per year
- proportion of nulliparous and multiparous women
- proportion of women per ethnic group
- proportion of home births
- rate of referral to secondary care

Characteristics of clients, collected by the midwife after the informed consent procedure:

- mother's date of birth, ethnic background, years of education, weight and height
- smoking (never, discontinued before current pregnancy, discontinued in first trimester, discontinued later in pregnancy; less than 10 cigarettes a day, 10-20, more than 20)
- alcohol use (no, discontinued before current pregnancy, discontinued in first trimester, discontinued later in pregnancy; sporadically, 0-2 units a day, more than 2)
- drug use (no, discontinued before current pregnancy, discontinued in first trimester, discontinued later in pregnancy; occasionally, daily, weekly, monthly)
- work status

Process measures

- % women declining participation
- % protocol violations
- % disagreements in primary outcome on verification by research assistant
- 3rd trimester US: intra-observer variability, inter-observer variability
- accuracy US: sensitivity, specificity of routine US to detect SGA
- Opinion of midwives towards effective and ineffective elements of intervention strategy

DATA COLLECTION

Existing databases

For all 15,000 women we will extract data from the following existing databases: 1) PRN database; 2) ultrasound centres' databases; 3) hospitals' patient records. These databases will be used to collect data on the primary clinical outcome 'severe adverse perinatal outcome' (e.g. Apgar score), obstetric variables, US scans (number, indication and findings, including biometry measures) and care processes (like number of days in hospital).

Forms and surveys

To collect data on variables that are not included in existing databases we will use the following forms and surveys.

Firstly, prior to onset of the study midwifery practices will fill in a short questionnaire on midwife practice characteristics as published in the practice's most recent LVR report.

Secondly, midwives will be asked to collect data on a small set of important prognostic variables for all women having signed the informed consent form (for example, on ethnicity, smoking, see p. 14).

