Both cost-effectiveness and cost-utility analyses will be done according to the intention-to-treat principle. ICERs and the ICUR will be calculated by dividing the difference in mean costs between the two groups by the difference between the two groups in effects and in QALYs, respectively. Bias-corrected and accelerated bootstrapping with 5000 replications will be used to estimate 95% confidence intervals around cost differences and the uncertainty surrounding the ICERs and ICUR. Uncertainty surrounding the ICERs and ICUR will be graphically presented on cost-effectiveness planes. Cost-effectiveness acceptability curves will also be estimated using the net benefit framework.[Stinnett & Mullahy, 1998] Cost-effectiveness acceptability curves show the probability that routine third trimester ultrasound screening to detect IUGR is cost-effective in comparison with usual care for a range of different ceiling ratios thereby showing decision uncertainty.

We will perform a subgroup analysis for women without US indication and for nulliparous women.

We will explore the robustness of the results of our intention to treat analysis by a per-protocol sensitivity analysis. Furthermore, we will repeat the pregnancy related cost-effectiveness analysis from a health care provider perspective and the cost-effectiveness analysis from a societal perspective using solely the data of the 600 randomly selected women participating in the survey study.

REFERENCES

Alfirevic Z, Stampalija T, Gyte GM. Fetal and umbilical Doppler ultrasound in high-risk pregnancies. *Cochrane Database Syst Rev* 2010a;(1):CD007529.

Alfirevic Z, Stampalija T, Gyte GM. Fetal and umbilical Doppler ultrasound in normal pregnancy. *Cochrane Database Syst Rev* 2010b;(8):CD001450.

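### The per-protocol rule requires a scan at 34-36 weeks in the intervention group but has no matching gestational condition for controls, so early events are removed from one arm only

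*Protocol*

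**What the plan says.** The per-protocol set is defined in the Protocol, Statistical analyses, Effectiveness analyses. It is "restricted to the women in the intervention group who received the two US examinations and to the women in the control group". The condition set for controls reads "to the women in the control group who did not receive any screening US". The analysis is additional to the intention-to-treat analysis.

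The scan timing is given twice. The synopsis says "two routine US examinations will be performed (between 28-30 weeks and 34-36 weeks". The section on control and intervention US strategies says "one between 28 and 30 weeks and one 6 weeks after the first US". The two agree, since 28-30 weeks plus 6 weeks is 34-36 weeks.

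Women are recruited at 20-22 weeks. In the primary outcome, deaths count from 28 weeks; the other components carry no minimum gestation.

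The economic section states: "We will explore the robustness of the results of our intention to treat analysis by a per-protocol sensitivity analysis". It gives no separate definition of per-protocol there.

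**The concern.** To have had both routine scans, a woman must still be pregnant in the 34-36 week window. To be a per-protocol control, she need only have had no screening scan, and no gestation has to be reached. Between 28 weeks and the second scan, an event disqualifies an intervention woman and leaves a control woman in the set. If anything, a short pregnancy makes it easier to qualify as a control, because there is less time in which to have a screening scan.

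The intervention arm must therefore survive a period that the control arm need not, and outcomes are counted during that period. At stake is the reading of the per-protocol result. It could appear to confirm a benefit, or it could make a null intention-to-treat result look like a matter of poor adherence. If the economic robustness check uses the same definition, it has the same tilt.

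**Working it through.** **The plan's own figures.** The protocol gives no number for the per-protocol analysis, so only its planning inputs can be checked. For 1.54% against 1.0%, 80% power and two-sided 0.05, the pooled two-proportion formula gives 6,749 per arm, or 13,498 in total (stated: 13,536, a difference of 0.3%). The design effect is 1 + (250 - 1) × 0.0003 = 1.0747, and 13,536 × 1.0747 = 14,547, as stated. The sample size is not in dispute.

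**Inputs from the protocol.** Event rate 1.54%; 7,500 women per strategy; design effect 1.0747. Expected events per arm: 7,500 × 0.0154 = 115.5.

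**Assumed inputs.** f is the share of events, and g the share of event-free women, dropped from the intervention arm only. The documents give neither.

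**Formula with no true effect.** The intervention arm keeps 0.0154(1-f) with events and 0.9846(1-g) without. The control arm keeps 0.0154 and 0.9846. The odds ratio is therefore (1-f)/(1-g). Example, f = 20% and g = 5%: 0.0154 × 0.80 = 0.01232; 0.9846 × 0.95 = 0.93537; rate 0.01232/0.94769 = 1.30%; odds ratio 0.80/0.95 = 0.84.

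| f | events dropped (115.5 × f) | g | intervention rate (control 1.54%) | null odds ratio | chance of a significant false benefit |
|---|---|---|---|---|---|
| 10% | 11.6 | 0 | 1.39% | 0.90 | 11.2% |
| 20% | 23.1 | 0 | 1.24% | 0.80 | 33.5% |
| 30% | 34.6 | 0 | 1.08% | 0.70 | 65.9% |
| 10% | 11.6 | 5% | 1.46% | 0.95 | 5.7% |
| 20% | 23.1 | 5% | 1.30% | 0.84 | 21.7% |
| 30% | 34.6 | 5% | 1.14% | 0.74 | 52.6% |

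The last column is the power of a two-proportion test at two-sided 0.05, with sample sizes divided by 1.0747. The nominal value in that direction is 2.5%, and f = g = 5% returns 2.5%. It ignores the adjusted multilevel model and is indicative only.

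**Direction.** f exceeds g exactly when the dropped women carry a higher event risk than the arm as a whole. Losses unrelated to outcome cancel. For example, if 15% of all intervention women miss a scan regardless of outcome, on top of f = 10% and g = 0, the ratio is (0.90 × 0.85)/(1 × 0.85) = 0.90, unchanged.

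**After correction.** If women whose pregnancies end early are either kept in both arms or removed from both arms, this source of imbalance disappears and the null odds ratio is 1.00.

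**The case against.** The strongest reply is about reach. All primary analyses, clinical and economic, are by intention to treat. Per-protocol is additional, and the economic section also plans a repeat in the 600 randomly selected women. That stands: the primary estimate, sample size and error rate are untouched.

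A second reply is about size. Women who decline or miss a scan are mostly event-free, so g = 0 is an extreme. With g = 15% and f = 10%, the ratio is 0.90/0.85 = 1.06, against screening. That also stands as a possibility, although it requires the dropped women to be at lower risk than those kept. The direction is therefore conditional on f exceeding g.

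Three stronger readings are tempting and are not supported:

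- **The artefact could equal the whole planned effect.** With g = 0, f = 35% gives an odds ratio of 0.65, close to the planned risk ratio of 1.0/1.54 = 0.65. That value of f is simply the one that yields this answer; nothing in the protocol shows it to be realistic. Several components, such as asphyxia and low Apgar score, are not specific to preterm birth.
- **Women referred out of primary care are dropped as well.** The protocol does not say whether scans done elsewhere count, and it draws on the records of ultrasound centres and hospitals. Only the loss of pregnancies that end before the second scan is certain.
- **The subgroup without an ultrasound indication has the same defect.** The plan says only "We will perform a subgroup analysis for women without US indication and for nulliparous women". A reader might infer from the data-extraction list, "US scans (number, indication and findings, including biometry measures", that status will be taken from third-trimester scans. That list defines no subgroup, and such a definition is commonly left to the SAP. Controls also receive scans on indication, so the direction would be unclear.

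**Conclusion.** The per-protocol definition is one-sided as written, and no other section of the protocol repairs it. The rule is stated explicitly, so an SAP that followed it would carry the selection forward. With no true effect, the odds ratio is about (1-f)/(1-g): 0.70 to 0.90 for f from 30% down to 10% with g = 0, and 0.74 to 0.95 with g = 5%. This assumes that the control exclusion for screening scans does not itself remove events selectively. The asymmetry follows from the wording; its size rests on f and g, which the documents do not give. The economic robustness check is affected if it uses the same definition. The definition should be corrected, but the flaw does not threaten the primary intention-to-treat conclusions.

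**What to change.** Preferred: count an intervention woman as per-protocol if she received every routine scan that fell due while her pregnancy was ongoing, and require an ongoing pregnancy at 28+0 weeks in both groups. State that a scan is missed only if its window closed with the pregnancy still ongoing; otherwise, births inside a window would again be lost from one arm. Early events after 28+0 weeks then stay in both groups.

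Alternative: apply one landmark, still pregnant at the second-scan window (best taken at its close), to both groups. The cost is that early events leave both arms, so the analysis describes later outcomes only.

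State that the per-protocol sensitivity analysis in the economic evaluation uses the same definition. It would also help to report how many women and events each criterion excludes, by group. The change takes a sentence or two and needs no new data. It should be settled before outcome data are examined. Neither version makes the per-protocol comparison a randomised one, so it remains supportive.
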